12.8.5. Analysis methods

1. Lesion counts
 - (i) The number of new or enlarging T2 lesions will be assessed from PD/T2 fast spin echo images.
 - (ii) New T1 hypo-intense lesion measures will be recorded as seen on the post-contrast T1 weighted spin echo scans.
2. Lesion volumes

A T2 and T1 lesion load calculation will be undertaken by an observer, blinded to the patient details using a semi-automated lesion contouring application programme.
3. Brain atrophy
 - (i) Percentage Brain Volume Change (PBVC) will be measured from volumetric T1 weighted scans using the SINA analysis application.
 - (ii) Regional atrophy measure using voxel-based morphometry (VBM), which is an unbiased automated technique designed to detect areas of grey matter atrophy independent of the anatomical constraints necessarily associated with *a priori* operator-defined region of interest analysis.
4. MTR
 - (i) *Lesion MTR maps* will be determined from the MT scan. White matter lesion masks will be outlined on the MT-off scan and the masks applied to the MTR map to calculate the lesional MTR at each time point. This measure is expected to reflect de- and re-myelination.
 - (ii) *GM and NAWM MTR*: As well as calculating the lesional MTR, grey and white matter masks will be segmented and applied to the MTR map to evaluate the mean normal appearing grey and white matter MTR value. Lesion masks will be removed in order to assess the non-lesional tissue.
5. Diffusion

Diffusion-based measures: Diffusion weighted images allow calculation of indices of structural integrity based on the diffusion coefficient of water molecules and their surrounding environment. These indices can reflect the underlying structural integrity as the hindrance and restriction of water molecules changes with disease.

13. STATISTICS AND DATA ANALYSIS

13.1 RATIONALE

The main aim of each national trial participating in this international collaborative effort, including the present one, is to assess the feasibility, safety and the toxicity of MSC infusion, as administered within this specific treatment protocol, in active MS. To fulfill this aim, all randomised patients receiving at least one MSCs infusion (or infusion media) will be followed for at least two years after the last study drug administration. All adverse events will be recorded and compared in the two treatment groups. Comparative analyses of the incidence of new GEL at MRI acquired on conventional 1.5 T MRI scans over 24 weeks will be conducted as well, to provide preliminary data on the activity of the experimental treatment. However, the main analyses of safety, toxicity and activity will be those on the entire data set obtained by pooling the results of all national trials, for an expected total of 160 randomised patients.

13.2 SAMPLE SIZE

Up to 23 patients are expected to be enrolled in the clinical trial for evaluation of the primary outcome (safety). Data from this clinical trial and from all other national trials will be pooled together for efficacy evaluation which will be evaluated as a decrease in the number of GEL (co-primary outcome).

A sample size of 160 patients was estimated to give an 80% power at a significance level of 5% to detect a decrease of 50% in the number of GEL counted during the 6 months duration of treatment. This number was estimated assuming that the average number of total GEL on 3 MRI scans (scan at weeks 4, 12 and 24) will be 7.4 (SD=11.4), that is half of the number of total number of GEL counted over 6 monthly scans in the phase 2 study of oral fingolimod for MS [43] .

13.3 EVALUATION OF PRIMARY OUTCOME VARIABLES

- Primary outcome: To assess the safety of intravenous therapy with autologous MSCs in MS patients. The safety of MSCs infusion will be evaluated including frequency, timing and severity of any adverse events in both MSCs and placebo treatment groups. A statistical comparison of the number of adverse events between treatment groups will be carried out using a chi-square test.
- Co-Primary outcome: To assess the activity of autologous MSCs in MS patients. The total number of gadolinium-enhancing lesions (GEL) at MRI at week 4, 12 and 24 will be compared between treatment groups using a Negative Binomial (NB) regression analysis, adjusting for the number of GEL at baseline.

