7. STUDY DESIGN

STREAMS is a randomised, double-blind crossover study comparing IV treatment with autologous MSCs vs. suspension media in MS patients with regards to the number of adverse events and new MRI activity (measured as GEL) at 24 weeks. A secondary analysis will compare the number of adverse events and GEL at weeks 0-23 and 24-48 within each treatment group (see Figure 1).

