7.1 STUDY OUTCOME MEASURES

Primary endpoints:

- number, timing and severity of adverse events in the MSC treatment group will be compared to the placebo group;
- total number of GEL counted over month 1, 3 and 6 will be compared between treatment groups.

[figure not shown]
Secondary endpoints:

- volume of GEL identified over months 1, 3 and 6 will be compared between treatment groups.
- number of GEL counted over months 7, 9 and 12 (crossover re-treatment) compared between treatment periods (placebo vs. active treatment) for each patient.
- combined unique MRI activity (number of new or enlarging T2, or enhancing or re-enhancing lesions).
- number of relapses in MSC treatment group vs. placebo group in the first 6 months and after crossover re-treatment in the two groups (see below for the definition of a relapse).
- time to sustained progression of disability (RRMS group) (see below for definition of sustained EDSS progression) and proportion of progression-free patients.

- proportion of disease-free patients (i.e. patients without relapses) and progression of MRI activity in the two groups.
- changes in the Multiple Sclerosis Functional Composite (MSFC) score in MSC treatment group compared to the placebo group.
- effect of MSCs on the peripheral immune responses (for patients in the first phase of recruitment).
- effect of MSCs on delayed type hypersensitivity (Type 1V hypersensitivity) reaction as measured by the Mantoux test.

Given the exploratory nature of MSC use, no specific quantitative assumptions have been made about the outcomes measures.

[figure not shown]
Figure 1: Patient flow and study outline

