13.4 EVALUATION OF SECONDARY OUTCOME VARIABLES

Secondary outcomes: To gather preliminary information about the efficacy of the experimental treatment in terms of combined MRI activity, incidence of relapses and disability progression.

- The total number of GEL lesions at MRI at weeks 4, 12 and 24 in the group originally randomised to placebo will be compared with the number of GEL lesions at MRI at weeks 28, 36 and 48 following the infusion using a mixed effect generalised model with NB errors.
- The dependence on time of the total number of GEL at MRI will be analysed in the group originally randomised to active treatment using a mixed effect generalised model with NB errors.
- Combined unique MRI activity (new or enlarging T2, or enhancing or re-enhancing lesions). The total number of new or enlarging T2, or enhancing or re-enhancing lesions at MRI at week 4, 12 and 24 post-treatment will be recorded in the two groups using a Negative Binomial (NB) regression analysis with the treatment group as covariate.
- Number of relapses in MSCs treatment group vs. placebo group will be acquired and using a Negative Binomial (NB) regression analysis with treatment group as covariate
- Time to sustained progression of disability (RRMS group) will be analyzed with a Cox proportional-hazards model
- Proportion of progression-free patients in two groups will be compared with the use of a chi-square test (RRMS patients).
- Mean changes in Multiple Sclerosis Functional Composite (MSFC) score in MSC treatment group vs. placebo group compared to baseline will be analysed with a one-way ANOVA test.

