13.6 DATA ANALYSIS

The number of GEL counted over 3 MRI scans will be considered a NB variable and analysed using a NB regression model. The model will be adjusted for the number of GEL on the baseline scan and will include treatment group as covariate. The number of relapses during the study period will be analysed with a NB regression model. Time to event variables will be studied with the Cox proportional-hazards model and visualised using the Kaplan-Meier survival curves. Proportion of events in the two treatment groups will be analysed by the chi-square test.

A paired-data analysis will be run to compare the number of GEL during the placebo and during the treatment arm in the group originally randomised to placebo, using both a parametric mixed model with NB errors and a non-parametric Wilcoxon test.

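### The primary safety test is a chi-square on the number of adverse events with no unit of analysis; counted by event it can inflate type I error, counted by patient it loses power

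*Combined protocol and SAP*

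**What the plan says.** Section 13.3, repeated in the study summary (section 4), says: "A statistical comparison of the number of adverse events between treatment groups will be carried out using a chi-square test". The endpoint in section 7.1 is also a number of events: "number, timing and severity of adverse events in the MSC treatment group will be compared to the placebo group".

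Two other passages bear on the unit. Section 13.6 has a general rule, "Proportion of events in the two treatment groups will be analysed by the chi-square test", with no denominator. Section 13.4 applies chi-square to a share of patients: "Proportion of progression-free patients in two groups will be compared with the use of a chi-square test".

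The plan's other per-patient lesion and relapse counts get a negative binomial (NB) model. GEL and combined MRI activity do, and for relapses section 13.6 says: "The number of relapses during the study period will be analysed with a NB regression model".

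On the window, section 7 frames the comparison "with regards to the number of adverse events and new MRI activity (measured as GEL) at 24 weeks" and adds: "A secondary analysis will compare the number of adverse events and GEL at weeks 0-23 and 24-48 within each treatment group". Sections 7.1 and 13.3 give no window for AEs. Section 13.1 says "All adverse events will be recorded and compared in the two treatment groups", directly after setting follow-up of at least two years from the last study treatment.

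This trial expects up to 23 patients (13.2). The main safety analysis pools the national trials, with 160 expected (13.1).

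**The concern.** A chi-square test needs a unit and a denominator, and here neither is given. Two analysts could run different tests and both would comply with the plan.

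If each event is a unit, the test assumes that events are independent. Repeat events in one patient are plausible. The AE definition in section 11.1 includes abnormal laboratory findings, and AEs are recorded at every scheduled visit (12.2), of which there are eight from week 0 to week 24, counting the 48/72-hour visit. A cluster of events in a few patients could then appear as a treatment difference.

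If the unit is the patient with at least one AE, independence holds, but a patient with one event and a patient with ten count the same.

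The window matters because treatments are reversed at the second infusion. After that, both randomised groups have received MSCs, and a comparison by randomised group no longer contrasts MSCs with placebo.

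**Working it through.** **Inputs from the documents.** N = 23 and N = 160 (13.1, 13.2). A 5% level is stated only for GEL (13.2).

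**Assumptions.** 5% two-sided for the safety test; 1:1 allocation (12 v 11 and 80 v 80); mean 0.5 to 10 AEs per patient; variance/mean ratio φ of 1 to 3. The documents give none of these for AEs.

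**1. The plan's own figure.** The pooled 160 is reproduced by an NB calculation for GEL.
- Dispersion: k = 7.4² / (11.4² − 7.4) = 0.447.
- n per group = (1.96 + 0.842)² × (1/7.4 + 1/3.7 + 2/0.447) / (ln 0.5)² = 79.7, so 80 per group and 160 in all.

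The variance/mean ratio assumed for GEL is therefore 11.4²/7.4 = 17.6. This does not carry over to AEs, but the sample size does rest on a strongly overdispersed per-patient count.

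**2. Events as the unit.** With equal groups the statistic is (A − B)/√(A + B), where A and B are the event totals. Its null variance is φ, while the test takes it to be 1. Hence

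type I error = 2 × [1 − Φ(1.96/√φ)],

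which does not contain N. Simulation of 200,000 null trials per scenario (NB counts, means 0.5 to 10) gives:

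| φ | Formula | N = 23, uncorrected | N = 160, uncorrected | N = 23, Yates | N = 160, Yates |
|---|---|---|---|---|---|
| 1 | 5.0% | 4.9–5.5% | 4.9–5.0% | 1.9–4.3% | 3.7–4.7% |
| 1.5 | 11.0% | 10.6–11.2% | 10.7–11.1% | 5.3–9.8% | 8.9–10.6% |
| 2 | 16.6% | 16.1–16.7% | 16.4–16.6% | 8.9–15.2% | 14.1–16.0% |
| 3 | 25.8% | 24.5–25.7% | 25.5–25.8% | 15.5–24.1% | 22.6–25.1% |

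The plan does not say whether a continuity correction applies. Pooling does not remove the inflation in either version.

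**3. Patients with at least one AE as the unit.** Type I error is at most 5.5% at 12 v 11 and 5.2% at 80 v 80. The cost is power. Take 80 v 80, placebo mean 2, φ = 3, and the rate doubled on MSCs.
- k = 2/(3 − 1) = 1. P(any AE) is 1 − (1 + 2)⁻¹ = 0.667 on placebo and 1 − (1 + 4)⁻¹ = 0.800 on MSCs. Power is 49%.
- Count model: SE of the log rate ratio = √[(1/2 + 1)/80 + (1/4 + 1)/80] = 0.185; ln 2/0.185 = 3.74; Φ(3.74 − 1.96) = 96%.

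Power for a doubled rate, patient-level chi-square against quasi-Poisson:

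| Size | Placebo mean | φ | Patient-level | Quasi-Poisson |
|---|---|---|---|---|
| 80 v 80 | 0.5 | 1.5–3 | 25–56% | 44–79% |
| 80 v 80 | 1 | 1.5–3 | 37–74% | 74–98% |
| 80 v 80 | 6 | 1.5–3 | 0–19% | about 100% |
| 12 v 11 | 2–6 | 2–3 | 0–12% | 22–83% |
| 12 v 11 | 1 | 1.5–3 | 9–16% | 9–25% |
| 12 v 11 | 0.5 | 1.5–3 | 8–14% | 1–9% |

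**4. Type I error of the replacement.** Quasi-Poisson with a t reference: 4.2–5.1% at 12 v 11 for means 2 to 10, conservative below that (2.3–4.0% at mean 1, 0.4–2.2% at mean 0.5), and 4.6–5.3% at 80 v 80. NB with a Wald test: 6.1–8.6% at 12 v 11 and 4.8–6.3% at 80 v 80. This is why the small analysis needs a different model from the pooled one.

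**The case against.** The best defence is that 13.3 should be read with 13.6 and 13.4. There chi-square is tied to proportions, once explicitly of patients, so a patient-level test may be what was meant, and type I error is then sound. The sizes also need overdispersion, which the documents do not establish. Section 5.2.3 reports an earlier series of 10 patients treated without any AEs, so low rates are possible. All of this stands, and it makes the percentages conditional. It does not supply the missing unit, and the patient-level reading has its own cost.

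Four stronger readings are tempting and not supported:
- *The safety test has a false-positive rate of up to 26%.* That needs events as the unit, φ = 3 and no continuity correction together. The plan states none of them.
- *The inflation would hide harm or wrongly stop the trial.* It produces false differences in either direction. No stopping rule uses this p-value, timing and severity are also evaluated, and a safety committee reviews side effects (15.3).
- *Unequal follow-up invalidates the count.* Withdrawn patients' data end at withdrawal (8.5) and an infusion can be delayed (8.4). But section 9.4 keeps following patients who stop treatment early, and 16.3 keeps those given other treatment in follow-up and analysis. No dropout rate is given, so this supports an offset and no more.
- *The primary comparison runs past crossover.* Section 7 says 24 weeks. Section 13.1 is loosely worded and should be reconciled with it.

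**Conclusion.** The concern holds as a gap in the definition of the first primary outcome's only named test. Taken literally, the wording gives type I error above 5% whenever AE counts are overdispersed: about 11%, 17% and 26% uncorrected at assumed ratios of 1.5, 2 and 3, at both sample sizes. With a continuity correction the figures are about 5–10%, 9–15% and 15–24% at 23 patients, and 9–11%, 14–16% and 23–25% at 160. Under Poisson counts or a patient-level unit there is no inflation, but the patient-level test gives up much of the power at the pooled size.

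That the unit is missing is certain. The sizes rest on assumed AE rates, dispersion, level and allocation. What is at stake is the reliability of the reported safety comparison, and the point should be fixed before the data are pooled.

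**What to change.** In 13.3 and the summary, replace the chi-square sentence with:

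*The number of AEs per patient will be compared by randomised group from first infusion to week 24 or the last observation before the second infusion, whichever is earlier; the same rule applies to patients who have no second infusion. A count model that allows for overdispersion will be used, with log person-time as offset: NB regression for the pooled analysis, and quasi-Poisson with a t reference distribution for the national analysis. The result will be a rate ratio with 95% CI. The numbers of patients with at least one AE and with at least one SAE will be reported alongside and compared by chi-square, or by Fisher's exact test where expected counts are small.*

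State the same window in 7.1 and 13.1. Keep section 7's within-group comparison as secondary, and report later events descriptively by time since MSC infusion.

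Costs:
- No new data are needed, since AEs per patient and infusion dates are already recorded.
- Confidence intervals widen by √φ: about 1.2, 1.4 and 1.7 times at ratios 1.5, 2 and 3.
- At about 0.5 to 1 AE per patient the count model gains little or nothing in the 23-patient analysis, and at 0.5 it has less power than the patient-level test.
- The offset assumes a roughly constant AE rate, which would fail if events cluster soon after infusion.
- Fisher's test is conservative at 12 v 11 (type I error 2–3%, against about 5% for chi-square).
- The wording must be agreed with the partner trials, because section 5.2.4 describes the protocol as identical across countries and the main analysis is pooled.

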5.2.4. Rationale for this study

Evidence from preclinical studies suggested that MSCs were an effective cell therapy for experimental autoimmune encephalomyelitis (EAE). In EAE, the IV injection of MSCs ameliorates the clinical course of acute disease and decreases demyelination, immune infiltrates and axonal loss, but has little or no effect in later stages of EAE. These results led to the conclusion that MSC administration should focus on individuals with on-going inflammation and before they develop irreversible disability. Pioneer small clinical studies in MS have already suggested their safety, thus paving the road from their clinical exploitation into larger phase II studies addressing their biological effect on markers of disease activity [39]. An international panel of MS neurology and stem cell experts, as well as immunologists formed an “International Mesenchymal Stem Cells Transplantation” (MSCT) Study Group with the aim to derive a consensus on the utilisation of MSCs for the treatment of MS along with protocols for the culture of the cells and the treatment of patients. This international consensus, based on the efforts of [name] (University of Genoa) and [name] (University of Ottawa), has been achieved and was published in 2010 [42]. In the consensus paper, the authors devised the synopsis of a phase I/II clinical trial, which will be fully adopted by scientists and clinicians belonging to the MSCT Study Group and presented to the respective national regulatory and funding agencies as single nation studies. This approach will enable the running of a series of parallel, independent but related, national studies adopting identical protocols, inclusion and exclusion criteria, primary and secondary outcomes collected on identical forms. The opportunity to pool the results of these studies will overcome the limitations of small phase I/II studies and provide enough statistical power to draw conclusions on the safety and efficacy of autologous MSCs transplantation in MS [42]. Our study will be conducted following the guidelines of the aforementioned consensus and utilise a protocol identical to the one adopted in other European countries and North America participating in this international collaborative effort. Identical, parallel but independent national trials will be conducted in Spain, Sweden, Denmark, France, Germany and Canada in order to assess the efficacy, safety and the toxicity of MSC infusion, as administered within this specific treatment protocol, in active MS. Evaluation of primary and secondary outcomes as well as exploratory outcomes will be carried out at the single national trial level but, more importantly, also on the entire data set obtained by pooling the results of all national trials, for an expected total of 160 randomised patients.

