18. PUBLICATION POLICY

The study primary outcomes will be pooled from all studies participating in the International Trial Consortium. All other outcomes and ancillary studies will be analysed and published independently or as seen appropriate by the Investigators. A writing group will be formed by all contributors who played a substantial role in the acquisition, analysis or interpretation of the data and will be chaired by the Principal Investigator. Authorship will be determined on the basis of the specific contribution to the study and to the article write-up. Minor contributions or paid technical work will be acknowledged as appropriate.

All publications and presentations relating to the study will be authorised by the Trial Management Group. The first publication of the trial results will be in the name of the Trial Management Group, if this does not conflict with the journal's policy. If there are named authors, these will include at least the trial's Chief Investigator, Statistician and Trial Coordinator. Members of the trial management group and the Data Monitoring Committee will be listed and contributors will be cited by name if published in a journal where this does not conflict with the journal's policy. Authorship of parallel studies initiated outside of the Trial Management Group will be according to the individuals involved in the project but must acknowledge the contribution of the Trial Management Group and the Study Coordination Centre. Authorship of publications resulting from this study will be based on generally accepted criteria for major medical journals.

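### Safety, the first primary outcome, is compared between groups only by a chi-square test for a difference; no interval or upper bound is planned, and the claim in 5.2.4 of enough power for safety has no calculation behind it

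*Combined protocol and SAP*

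**What the plan says.** Section 13.3 describes the safety outcome in two sentences. The first is descriptive: "The safety of MSCs infusion will be evaluated including frequency, timing and severity of any adverse events in both MSCs and placebo treatment groups". The second names the inference: "A statistical comparison of the number of adverse events between treatment groups will be carried out using a chi-square test". The study summary (section 4) repeats both. Section 7 adds a secondary comparison of adverse events in weeks 0–23 and 24–48 within each treatment group, without naming a method.

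On sample size, section 13.2 gives up to 23 patients for safety, with no power or precision figure, and says: "Data from this clinical trial and from all other national trials will be pooled together for efficacy evaluation". Section 13.1 puts the safety analysis elsewhere: the "main analyses of safety, toxicity and activity will be those on the entire data set obtained by pooling the results of all national trials", with 160 expected. Section 18 agrees with 13.1: "The study primary outcomes will be pooled from all studies participating in the International Trial Consortium". Section 5.2.4 says that pooling will "provide enough statistical power to draw conclusions on the safety and efficacy of autologous MSCs transplantation in MS".

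No section gives an expected adverse event rate, a tolerable excess, a confidence interval or an upper bound. Section 7.1 says that no quantitative assumptions were made about the outcome measures. The one numerical limit on harm for the study as a whole is the mortality trigger for early closure in 12.5.1, which is not an analysis of the safety outcome.

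**The concern.** A chi-square test takes no difference as its null hypothesis. A significant result signals harm. A non-significant one says only that the data are compatible with no difference, and in a small trial they may also be compatible with a large excess. Without an interval or bound, the report need not say how large an excess remains possible. That is the quantity a reader of an early-phase safety trial needs.

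Two things are at stake. The first primary question may be answered with a p-value that carries little information. And section 5.2.4 may lead readers to think that the pooled data set was sized for safety, when the only calculation in the plan concerns GEL.

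**Working it through.** **1. The plan's own figure.** Section 13.2 gives a mean of 7.4 GEL (SD 11.4), a 50% decrease, 5% significance and 80% power. For a negative binomial log rate ratio (two-sided):

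- dispersion = (SD² − mean)/mean² = (129.96 − 7.4)/54.76 = 2.238
- n per arm = (1.960 + 0.842)² × (1/7.4 + 1/3.7 + 2 × 2.238)/(ln 0.5)² = 7.849 × 4.882/0.4805 = 79.7, so 80 per arm and 160 in total.

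The 160 reproduces from the GEL inputs alone. No safety input enters it.

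**2. Power of the safety test.** The documents give no event rates and no allocation ratio, so these are assumed: 1:1 allocation (12 v 11, either way round, for 23 patients; 80 v 80 for 160), the unit is the patient with or without the event, and the test is the uncorrected chi-square at two-sided 5%. Power is the sum, over all tables with chi-square at or above 3.84, of the product of the two binomial probabilities.

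| Placebo v MSC rate | 23 patients | 160 patients |
|---|---|---|
| 2% v 10% | 2% | 57% |
| 5% v 10% | about 1% | 21% |
| 5% v 15% | 4–5% | 57% |
| 5% v 20% | 10–12% | 85% |
| 10% v 20% | about 7% | 42% |
| 20% v 40% | 18–20% | 80% |
| 50% v 75% | 22–26% | 91% |
| 20% v 60% | about 50% | over 99% |

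From a 5% placebo rate, 80% power needs an MSC rate of about 53% with 23 patients and about 19% with 160.

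**3. What a non-significant result can hide.** Take 3 of 11 patients with an event on MSC and 0 of 12 on placebo.

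- Chi-square = 23 × (3 × 12 − 8 × 0)²/(11 × 12 × 3 × 20) = 29,808/7,920 = 3.76, p = 0.052.
- Wilson 95% limits are 9.8% to 56.6% for 3/11 and 0 to 24.3% for 0/12.
- Newcombe lower limit: 0.273 − √[(0.273 − 0.098)² + 0.243²] = −0.03. Upper limit: 0.273 + (0.566 − 0.273) = 0.57.

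The test says not significant; the interval says that an excess of up to 57 points is not excluded.

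**4. What bounds would show.** With no events among n exposed patients, the exact one-sided 95% upper bound is 1 − 0.05^(1/n):

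- n = 12 (MSC in period 1, national trial): 22.1%
- n = 23 (all infused with MSC over both periods): 12.2%
- n = 80 (MSC in period 1, pooled): 3.7%
- n = 160 (all infused with MSC over both periods, pooled): 1.9%

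**The case against.** The strongest reply has four parts.

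- **No rule equates non-significance with safety.** A reader might infer that the plan will read p > 0.05 as safe. No section says so, and 13.3 sets the test beside a description of frequency, timing and severity. This stands: the gap is a missing quantity, not a wrong decision rule.
- **The chi-square is not the only look at safety.** Section 7 has the within-group comparison, 10.6 defines infusion toxicity numerically, 15.3 has a safety committee review both arms, and 13.1 plans at least two years of follow-up. This also stands, so the plan does not reduce to one p-value. But none of these provides an interval or a bound.
- **The main safety analysis is the pooled one.** Section 13.1 says so and section 18 agrees, and at 160 patients large excesses are well covered. This limits how far the figures for 23 can be pressed. Section 13.2, however, assigns the 23 to safety and pooling to efficacy, so the passages must be reconciled. Pooling supplies no interval either.
- **The power figures rest on chosen rates.** True. At 23 patients they run from about 1% to about 50% across the rates tabulated, so no single miss rate can be stated as a property of the trial.

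Low power for adverse events is usual in phase II. That is a reason to report intervals rather than to rely on a test.

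**Conclusion.** The point holds as a gap in the planned analysis. The between-group safety inference is a test for a difference, and nothing planned would show how much excess harm has been excluded. With 23 patients, power is 26% or less for excesses of 5 to 25 points at the rates tabulated. With 160, power is 80% or more for the tabulated excesses of 15 points and above, but 42–57% for 2% v 10%, 5% v 15% and 10% v 20%. These figures assume 1:1 allocation, one yes-or-no outcome per patient and event rates that the documents do not give.

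The safety half of the power statement in 5.2.4 has no calculation behind it. A reader might go further and infer that 160 patients are too few for safety in general. That does not follow: about 5% v 19% is detectable with 80% power, and common harms are covered. What can be said is that adequacy for safety was not calculated and depends on the size of excess that matters, which the plan does not state.

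**What to change.** In 13.3 and the study summary, base the safety conclusion on estimation, for both the national and the pooled data set:

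- (a) Report the MSC-minus-placebo difference in the proportion of patients with any adverse event, and with any serious adverse event, over weeks 0–24, with a 95% confidence interval (Newcombe or exact).
- (b) Report an exact one-sided 95% upper bound for the incidence of each type of serious adverse event after MSC infusion, and state the number exposed. The denominator matters: with no events in the national trial the bound is 22.1% on period 1 alone, and 12.2% only if all 23 receive MSC.
- (c) State that a non-significant comparison is not evidence of safety, and that the conclusion will quote the largest excess not excluded.

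The chi-square can stay as a supporting result. In 5.2.4, limit the power claim to GEL, or state what excess 160 patients can detect (about 5% v 19% at 80% power, under an assumed 5% placebo rate).

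The cost is a few lines of text and analysis, with no extra patients or data. The drawback is that the safety statement will be visibly less reassuring.
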